**3.5.2.3 Figure 2: Breakdown of educational intervention compared to the current standard of care.**

**3.5.2.4 Adherence**

An initial face-to-face session will take place at the initial visit with each subsequent visit either in person or via telephone. Points that will be highlighted are the importance of following study guidelines. Monetary incentive of a 10 dollar Tim Hortons gift card will be given for each survey the study participant completes in order to encourage continued engagement in the study. The gift cards will be given in person at the first session and the other gift cards will be sent in the mail once the final survey has been completed.

### **3.5.2.5 Concomitant Care**

All patients will be seen in a tertiary level clinic. Clinicians are blinded to the allocation of the study participants. Therefore, regardless of their study allotment they will receive the current standard of care provided in the clinic.

### **3.5.3 Outcomes**

#### **3.5.4 Primary Outcome Measures**

Targeted education provided to patients suffering from post-traumatic headache will be assessed using the RPQ. The RPCSQ is a 16-question instrument that examines post-concussion symptoms rated by the patient according to the increase in their frequency compared with premorbid levels. The total score is calculated based on 2 domains (cognitive and emotional-somatic) and ranges from 0 to 72. The RPQ has been shown to measure severity of postconcussion symptoms reliably with good test-retest and inter-rater reliability for individual symptom scores. Based on previous studies, splitting the RPQ into two subscale scores: RPQ-3 uses the sum of scores from three items (headaches, dizziness and nausea) and RPQ-13 uses the sum of scores of the other 13 items. Higher scores especially for the RPQ-13 subscale are associated with greater impact on lifestyle. For our study significance will be observed if patients reported symptoms decreased by 3 on the RPQ-3 and 10 on the RPQ-13.

#### **3.5.5 Secondary Outcome Measures**

For the secondary endpoints, we will analyze the frequency and type of health care patients accessed outside of their current standard of care during the 12-week study period. This will be compared to our controls and will include emergency room, family physician visits, hospital admissions and telehealth that are related to post traumatic headache symptoms.

Another end point we are interested in exploring is whether patients that are provided targeted headache education along with tertiary care has an increased frequency of social interactions in comparison to patients receiving the current standard of care. We are very interested in the hours that each patient devotes to their previous work or hobbies and we will be comparing this once again to patients in the clinic who are receiving the standard of care. This outcome will be measured using the PART-0 tool which asks questions about the type and frequency of social engagements that patients may encounter each week along with the hours that patients devote to returning back to work, school or homemaking.

Lastly, we are interested in whether or not education and reassurance alter a patient's perceived quality of life after a mild-traumatic brain injury. This will be analyzed by using the QOLIBRI (Quality of Life after Brain Injury). Using this scale we hope to capture whether or not patients believe they play an active role in their health and whether or not they feel empowered to alter their health status. It will hopefully also allow us to capture what

barriers there are to a patient's recovery in regard to what negative feelings and limits they perceive; preventing them from making a meaningful recovery.

### **3.5.6 Sample Size**

Sample size is based on alpha (2-sided significant level) of 0.05 and power of 80%. Given that the largest review study (Theeler, 2013) showed a headache prevalence of 21-100% (0.21 – 1.00) in their TBI group and 26% (0.26) in the control group with a ratio of control/cases= 1:1, sample size was computed at 28 (Educational group) and 28 (standard of care group) with total sample size of 56. We have anticipated 20% attrition and therefore we will aim to enroll 35 patients per study arm in order to maintain statistical significance. This rate is based on prior studies using the RPQ and a recent study conducted at St. Michael's by Hu et al. looking at age and association with mild-traumatic brain injury symptoms.

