### **3.5.7 Recruitment**

Subjects will be recruited by individuals in the patient's circle of care including the emergency department triage nurse. Patients with mild traumatic brain injury will be enrolled at least 12 weeks after their injury. Recruitment of study participants fulfilling eligibility criteria will be identified and referred through the emergency room, their primary care physician or specialist to the St. Michael's head injury clinic in Toronto between January and December 2018.

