### ***3.7.3 Primary Outcomes.***

Data will be collected using the Rivermead Post Concussion Symptoms Questionnaire (RPQ): The symptoms listed on the RPQ are those most commonly reported in the published literature as post concussion syndrome (PCS). The RPCSQ is a 16-question instrument that examines post-concussion symptoms rated by the patient according to the increase in their frequency compared with premorbid levels. The total score is calculated based on 2 domains (cognitive and emotional-somatic) and ranges from 0 to 72. The RPQ has been shown to measure severity of postconcussion symptoms reliably with good test-retest and inter-rater reliability for individual symptom scores. Based on previous studies, splitting the RPQ into two subscale scores: RPQ-3 uses the sum of scores from three items

(headaches, dizziness and nausea) and RPQ-13 uses the sum of scores of the other 13 items. Higher scores especially for the RPQ-13 subscale are associated with greater impact on lifestyle. For our study significance will be observed if patients reported symptoms decreased by 3 on the RPQ-3 and 10 on the RPQ-13.

We will be comparing headache symptom reporting between the two groups assigning significance if patients in the education arm have a decrease in symptom reporting on the RPQ-3 by 3 and 10 on the RPQ-13.

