#### **3.7.7 Statistics**

The IBM SPSS statistical software will be used for the data analysis. Data will be entered on demographic factors (sex, age, ethnicity, years of education), frequency and type of health care accessed will be analyzed as well. Scores on the Rivermead, PART-O and QUOLIBRI will be analyzed and comparisons will be made between the educational arm and the current standard of care group. We will be using univariate Chi-square analysis for categorical variables and 1 way analysis for continuous variables to assess for significant difference. P-value of <0.05 will be considered as statistically significant.

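### The 28 per arm at 80% power comes from headache prevalence in TBI versus control groups, not from the RPQ difference between education and standard care, so the stated power does not apply to the primary comparison

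*Protocol*

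**What the plan says.** Section 3.5.6 sets a two-sided alpha of 0.05 and 80% power. It takes a headache prevalence of 0.21 to 1.00 from a review, "in their TBI group and 26% (0.26) in the control group with a ratio of control/cases= 1:1", and concludes that "sample size was computed at 28 (Educational group) and 28 (standard of care group) with total sample size of 56". Allowing for 20% attrition, it plans to enrol 35 per arm.

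The rest of the protocol describes a different comparison:

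- **Population.** Section 3.5.7 says "Patients with mild traumatic brain injury will be enrolled at least 12 weeks after their injury". Section 3.2 places both groups in the chronic phase of post-traumatic headache.
- **Primary endpoint.** Section 3.3.2 asks about decreases of 3 points on the RPQ-3 and 10 on the RPQ-13, with education compared with no education. Section 3.5.4 repeats the thresholds: "For our study significance will be observed if patients reported symptoms decreased by 3 on the RPQ-3 and 10 on the RPQ-13". Section 3.7.3 says "We will be comparing headache symptom reporting between the two groups assigning significance if patients in the education arm have a decrease" of those sizes.
- **Analysis.** Section 3.7.7 says of the Rivermead, PART-O and QOLIBRI scores that "comparisons will be made between the educational arm and the current standard of care group".

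**The concern.** The review's two groups are people with and without TBI. The trial's two groups are both people with mild TBI, randomised to education or usual care. Neither trial arm corresponds to the 0.26 control group, yet section 3.5.6 gives the resulting numbers to the educational and standard-of-care groups as if they did.

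The outcome differs as well. Headache prevalence is not an endpoint of this trial, while the RPQ-3 and RPQ-13 are sum scores, whose power depends on a difference and an SD. Section 3.5.6 gives neither.

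A reader will take the 80% as the chance of detecting the 3-point and 10-point effects. It is not that, so a non-significant RPQ result could not be read against it. The figure is also the only stated justification for enrolling 70 people.

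**Working it through.** **1. The protocol's own calculation.** Inputs from section 3.5.6: two-sided alpha 0.05 (z = 1.960), power 80% (z = 0.842), 1:1 allocation, p₂ = 0.26, p₁ somewhere in 0.21 to 1.00.

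Unpooled: n = (1.960 + 0.842)² × [p₁(1−p₁) + p₂(1−p₂)] / (p₁−p₂)², where (1.960 + 0.842)² = 7.849.

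Pooled: n = [1.960√(2p̄(1−p̄)) + 0.842√(p₁(1−p₁) + p₂(1−p₂))]² / (p₁−p₂)², where p̄ = (p₁+p₂)/2.

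| p₁ | n per arm, pooled | n per arm, unpooled |
|---|---|---|
| 0.21 | 1,127.7 | 1,124.9 |
| 0.40 | 175.9 | 173.2 |
| 0.50 | 63.0 | 60.3 |
| 0.605 | 31.2 | 28.4 |
| 0.70 | 19.0 | 16.3 |
| 1.00 | 5.3 (6 needed) | 2.8 |

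At 0.26 there is no difference and no finite n. At 0.21 the difference has the opposite sign.

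Solving for n = 28 gives p₁ = 0.608 (unpooled), 0.624 (pooled), 0.623 (arcsine) or 0.659 (continuity-corrected). The protocol states none of these. The midpoint of its range, (0.21 + 1.00)/2 = 0.605, gives 7.849 × 0.431375 / 0.345² = 28.4 with the unpooled formula. That plausibly explains the 28, but the text does not say the midpoint was used.

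The attrition step reproduces: 28 / (1 − 0.20) = 35 per arm, 70 in total.

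**2. What 28 evaluable per arm gives on the RPQ.** For a two-sample t-test at two-sided 0.05 (noncentral t), 80% power at 28 per arm needs a standardised difference of 0.762. The largest SDs compatible with 80% power are therefore:

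- RPQ-3: 3 / 0.762 = 3.9
- RPQ-13: 10 / 0.762 = 13.1

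**3. Power over a range of SDs.** The protocol gives no RPQ SD, so those below are assumptions.

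| Subscale (difference) | Assumed SD | Power at 28 per arm | n per arm for 80% |
|---|---|---|---|
| RPQ-3 (3 points) | 3 | 96% | 17 |
| | 4 | 79% | 29 |
| | 5 | 60% | 45 |
| | 6 | 45% | 64 |
| RPQ-13 (10 points) | 11 | 92% | 21 |
| | 14 | 75% | 32 |
| | 15 | 69% | 37 |
| | 18 | 53% | 52 |

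**4. If both subscales must succeed.** Treating the two test statistics as bivariate normal, 80% power on each gives joint power of 0.80 × 0.80 = 64% at correlation 0 and 71% at correlation 0.7. At SDs of 4 and 14, joint power is 0.787 × 0.747 = 59% at correlation 0 and 67% at 0.7.

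**The case against.** Several points can be made for the protocol.

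- **The size may be adequate.** At SDs of 3.9 and 13, power is about 81% on each subscale. This stands: the defect is an unsupported power statement, not a demonstrated shortfall.
- **The endpoint could be a responder criterion.** Sections 3.5.4 and 3.7.3 speak of patients having a decrease of 3 and 10, and section 3.7.7 plans chi-square tests for categorical variables. On that reading a two-proportion formula is the right type, and the SD limits above would not apply. However, section 3.3.2 words the objective as a comparison with those not educated, and section 3.7.7 compares scores between arms. Even for a responder endpoint, TBI-versus-control headache prevalence would be the wrong input.
- **The larger RPQ-3 SDs are pessimistic.** Section 3.5.4 gives a 16-item total of 0 to 72. With equal item ranges (72/16 = 4.5 per item), the RPQ-3 spans 0 to 13.5. A uniform spread over that has SD 13.5/√12 = 3.9, and a single-peaked distribution has at most 13.5/3 = 4.5. SDs of 5 and 6 are therefore unlikely for week-12 scores, though possible for change scores when week 0 and week 12 correlate weakly. Those rows are the unfavourable end.
- **Section 3.5.6 does mention prior RPQ studies.** That sentence follows the attrition figure and most naturally refers to it. It supplies no difference or SD.
- **The success rule may be left to the SAP.** This is fair, so joint power is given only conditionally. Correlation 0 is a floor, since both subscales come from one questionnaire.

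**Conclusion.** The concern holds. The 80% power in section 3.5.6 belongs to a comparison of headache prevalence between TBI and control groups, which this trial does not make. Power for the RPQ-3 and RPQ-13 comparison is not stated and cannot be derived from the protocol.

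The size of the gap depends on SDs that the protocol does not supply. At 28 evaluable per arm, 80% power per subscale holds up to the limits of 3.9 and 13.1 and falls away above them. This assumes that 3 and 10 points are between-arm mean differences and that each subscale is tested with a two-sample t-test at two-sided 0.05. Nothing here shows that the trial is underpowered. It shows that the stated justification does not support the claim, and this must be corrected.

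**What to change.** Rewrite section 3.5.6:

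1. Replace the prevalence calculation with one for the between-arm difference in RPQ-3 (3 points) and RPQ-13 (10 points).
2. Use an SD with a named source, of the kind the analysis will use (week-12 score or change from week 0).
3. Restate power at the planned 28 evaluable per arm.
4. State whether both subscales must succeed and, if so, give the joint power and the correlation assumed.
5. If no SD can be sourced, state that 80% power per subscale holds only for SDs up to 3.9 and 13.1, and show power over a range of SDs.

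If a responder endpoint is intended, say so and base the calculation on responder proportions in the two randomised arms.

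The cost is one paragraph, and the stated power may look less favourable. Restating power at 28 evaluable per arm needs no added enrolment. If the sourced SDs exceed the limits, the sponsor must either accept and state the lower power or enrol more than 35 per arm. Enrolling more could be costly: section 3.5.7 planned recruitment for January to December 2018, and this version is dated April 16, 2019, so recruitment might have to be reopened.

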### **3.5.7 Recruitment**

Subjects will be recruited by individuals in the patient's circle of care including the emergency department triage nurse. Patients with mild traumatic brain injury will be enrolled at least 12 weeks after their injury. Recruitment of study participants fulfilling eligibility criteria will be identified and referred through the emergency room, their primary care physician or specialist to the St. Michael's head injury clinic in Toronto between January and December 2018.

## **3.6 Methods: Assignment of Intervention**

### **3.6.1 Allocation**

Participants will be randomly assigned to either control or interventional group with a 1:1 allocation as per a computer-generated randomization schedule using permuted blocks of random sizes. The block sizes will not be disclosed, to ensure concealment. The research assistant will not be allowed to touch the randomizing envelopes until each patient is about to be randomized.

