**3.5.2.2 Summary of education by session: PowerPoint slides will be split into three distinct sections.**

*Initial session: (0 weeks): (In person)* We will outline the study. Approximately 30 minutes in duration.

[figure not shown]
- Review inclusion/exclusion criteria
- Explain study goals
- Obtain written/verbal informed consent
- We will cover topics such as defining the basic anatomy and the consequences of head trauma. We will include common symptoms along with when to seek medical guidance, medications to avoid and helpful lifestyle and treatment tips. Patients will be provided with links to approved websites.
- Prior to this session
  - Complete demographic information, medical history, trauma history and participant contact information (email or phone) will be gathered. If patients are identified in the ER, this information will be provided by the Triage nurse and forwarded to the research assistant who will be responsible for follow-up and providing the study materials.
  - Rivermead Post-Concussive Questionnaire (RPCSQ), PART-O and QOLIBRI (Yellow form: See Appendix) will be completed.
- *Second Session (6 weeks): (via email)*. Explain importance of keeping brain active; define the assessment of brain activity. 10-20 minutes to review the PowerPoint. Follow up will be done 1 week later either in person, email or via telephone to ensure patients are able to open the PowerPoint and have reviewed the literature. There will be no education or discussion about current treatment regimen or symptoms. Should a patient have questions regarding their current treatment plan or symptoms, our volunteers will put patients in contact with the Head Injury Nurse. All calls will be made during clinic hours in order to help facilitate communication with the clinic.

*Third Session (12 weeks)- (In person or sent via email)* We will explain importance of stress, sleep, and exercise on brain function, define the influence of lifestyle on recovery.

Approximate duration is 10-20 minutes. 1 week later follow up via telephone or email will occur by the methods listed above to ensure that the patient was able to open the PowerPoint. At this time we will:

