- Re-verify inclusion criteria to be done by Research Assistant. There will be no education or discussion about current treatment regimen or symptoms. Should a patient have questions regarding their current treatment plan or symptoms all calls will be made when the Head Injury Nurse is available to connect with patients directly.

- Rivermead Post-Concussive Questionnaire (RPCSQ), PART-O and QUOLIBRI will be completed via telephone or email and entered via REDCap into our database. Survey data will be uploaded by student or research assistant that is unaware of the patient's randomization.
- The patients who did not participate in the education seminar will fill out surveys at week 0 and 12.

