### **3.6.2 Blinding**

Assessments regarding clinical recovery will be conducted by an assessor who is aware of the allocation of the patients in the study. The assessor will have a template in which to follow in order to ensure that the only difference between the two groups will be to ensure that the educational arm is able to open the pdf. Those who work in the clinic will not know

the allocation of the patient in the study but we are aware that this may be discovered during clinic visits. This will be a variable to consider when we analyze the data. An employee outside the research team will feed data into the computer in separate datasheets so that the researchers can analyze data without having access to information about the allocation

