### **3.8 Ethics and dissemination**

#### **3.8.1 Ethics**

If the patient is interested in this study, they will receive the consent form explaining the purpose, procedure and requirements of the project from trained research assistants who will be available to answer questions regarding the project. Informed consent will be obtained from patients who will meet the eligibility criteria and agree to participate.

If the participant cannot sign and date the consent form properly they will be asked to provide consent with an "X", their initials or by signing with their alternate hand. If the participant is completely unable to provide written consent they will be asked for verbal consent and research staff obtaining consent will document the discussion on the consent form. Initial information will be extracted from the medical record including age, medical history, imaging results, Glasgow coma scale and neurological examination. Patients who agreed to participate will be asked to complete a demographic questionnaire, the Rivermead Post Concussion Symptom Questionnaire, the QUOLIBRI and the PART-O in person for the first session and then either again in person or by telephone interview.

Participant involved in the educational arm of the study must have email and easy access to a computer. When they are randomized they will be asked for their email address.

Participants will be given their study ID number when they consent. They will be asked to use this number as their ID on the survey. Follow up at 7 weeks will occur with the education arm 1 week after they have been emailed the power point material.

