## **3.9 Appendices**

1. Consent to Participate in a Research Study
2. Yellow Baseline Questionnaire: Includes Rivermead, PART-O and QUOLIBRI
3. Blue follow up Survey: Included Rivermead Post Concussion Symptoms Questionnaire (RPCSQ), PART-O and the QUOLIBRI
4. Post Concussion Headache Assessment
5. Control and Study Participant Master Lists

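### Section 3.6.1 credits undisclosed block sizes with ensuring concealment, but enrolment is not separated from envelope handling, and anyone who sees past assignments can guess the next arm better than chance

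*Protocol*

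**What the plan says.** Protocol section 3.6.1 describes a "1:1 allocation as per a computer-generated randomization schedule using permuted blocks of random sizes" and adds: "The block sizes will not be disclosed, to ensure concealment". Its other safeguard is a rule on handling: "The research assistant will not be allowed to touch the randomizing envelopes until each patient is about to be randomized". The protocol does not say who holds the envelopes, or whether they are sealed, opaque or numbered.

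The staff roles are spread over several sections:

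- **Consent (3.8.1):** patients who are interested will find that "they will receive the consent form explaining the purpose, procedure and requirements of the project from trained research assistants".
- **Materials and follow-up (3.5.2.2):** for patients identified in the ER, baseline information is "forwarded to the research assistant who will be responsible for follow-up and providing the study materials".
- **Week-0 session (3.5.2.2):** eligibility review, consent and the first education content are listed under the same in-person session. The person who runs it is not named.
- **Assessment (3.6.2):** done by "an assessor who is aware of the allocation of the patients in the study".
- **Survey data (3.5.2.2):** "uploaded by student or research assistant that is unaware of the" allocation.
- **Recruitment (3.5.7):** by people in the patient's circle of care, including the ER triage nurse.

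Section 3.7.2 describes a REDCap database built by the Applied Health Research Centre at the same hospital. It is not used for allocation.

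**The concern.** Concealment means that whoever decides whether a patient enters cannot anticipate the arm. Undisclosed random block sizes hide where each block ends. They do not hide the running tally, which returns to zero at the end of every block whatever its size. A person who sees earlier assignments can therefore name the arm that is behind and be right more often than not.

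The rule against touching envelopes early guards against looking ahead. It does nothing about inference from past assignments, and it leaves the envelopes with a research assistant at the moment of randomisation.

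The risk is selection bias. Some eligibility and consent decisions involve judgement, for example whether a patient is medically stable. If these were influenced by the expected arm, the groups could differ in prognosis before any education is given. The outcomes (RPQ, PART-O, QOLIBRI and recalled health-care use) are all patient-reported, and the chi-square and one-way comparisons in 3.7.7 would not remove such a difference.

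**Working it through.** The protocol states no figure for predictability, so there is none to reproduce.

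**Inputs.** From the protocol: 1:1 allocation in permuted blocks of random size (3.6.1), 70 patients, and 28 per arm after attrition (3.5.6). Assumed, because the protocol does not give them: block sizes between 2 and 10, how many assistants see assignments, and how strongly enrolment is steered.

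**Step 1: fixed blocks.** For a block of size b, a person who always names the lagging arm, and guesses at random when the tally is even, is right in a proportion

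[b/2 + (2^b / C(b, b/2) − 1)/2] / b.

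For b = 4 this is [2 + (16/6 − 1)/2]/4 = 70.8%. For b = 2, 6, 8 and 10 it is 75.0%, 68.3%, 66.6% and 65.3%.

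**Step 2: random block sizes.** Sequences of 70 were simulated with no knowledge of any block size. The columns for two and three assistants assume that patients fall to them at random and that each sees only their own assignments. Each cell there gives two rules: naming the arm behind in one's own tally, then naming the opposite of one's own last assignment.

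| Block sizes | One person sees all | Two assistants | Three assistants |
|---|---|---|---|
| 2, 4 | 72% | 53.9 / 60.1% | 52.8 / 57.2% |
| 2, 4, 6 | 70% | 53.8 / 58.3% | 52.6 / 56.2% |
| 4, 6 | 69% | 53.9 / 57.5% | 52.8 / 55.9% |
| 4, 6, 8 | 68% | 53.9 / 56.6% | 52.7 / 55.3% |
| 6, 8, 10 | 66% | 53.7 / 55.3% | 52.7 / 54.5% |

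An enroller who sees no earlier assignment is right 50% of the time.

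**Step 3: does hiding the sizes help?** For sizes 4 and 6, the lagging-arm guess is right 69.1% of the time without the sizes and 69.1% with every size known. The average rate is unchanged.

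**Step 4: possible bias.** Let c be the total prognostic contrast, in SD, between patients enrolled when education is expected and those enrolled when control is expected. Let p be the overall proportion of correct guesses. The expected difference between arms with no education effect is c × (2p − 1). For blocks of 2, 4 and 6 with one fully informed enroller, p = 0.701:

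- c = 0.25: 0.25 × 0.402 = 0.10 SD
- c = 0.50: 0.50 × 0.402 = 0.20 SD

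For a two-sided 5% t test with 28 per arm, the noncentrality is the bias × √(28/2). That is 0.374 for 0.10 SD, giving a rejection rate of 6.6%, and 0.748 for 0.20 SD, giving 11.4%. With p = 0.60, the top of the range for assistants who do not share assignments, c = 0.25 gives 0.25 × 0.20 = 0.05 SD.

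**The case against.** The strongest reply is that the protocol nowhere says that the same assistant takes consent, opens envelopes and sees every earlier assignment. Section 3.8.1 speaks of assistants in the plural and 3.6.1 of one. The sentence on providing materials in 3.5.2.2 concerns patients identified in the ER, and the same section has survey data uploaded by someone unaware of allocation. Part of the selection sits with referring clinicians and the triage nurse (3.5.7). Clinic staff are meant to be blinded (3.5.2.5), although 3.6.2 accepts that they may discover the arm. All of this stands. It limits the point to roles that are not separated; it does not show that they are separated.

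Four stronger readings are tempting, and the documents do not support them:

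- **A flat 70% guessing rate.** It needs small blocks, whose sizes are not stated, and one person tracking the whole sequence.
- **An inflated error of 11%.** It needs a 0.50 SD contrast applied at every uneven tally. No document gives evidence of any steering.
- **Email as a motive for steering.** Section 3.5.1.1 requires email access of every participant. Only easy access to a computer is stated for the education arm alone (3.8.1).
- **Lists that reveal the arm.** "Control and Study Participant Master Lists" is only an appendix title in 3.9; its contents and who may see it are not shown. The linking log described in 3.7.1 holds name and study ID.

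It is also fair that random sizes do some good: they limit how often an assignment can be known for certain. For someone who knows the set of possible sizes, the share is about 2–11% across the mixes tried.

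**Conclusion.** The point holds in a limited form. Undisclosed block sizes cannot by themselves ensure concealment, and the protocol does not separate those who enrol from those who handle envelopes and learn the arms. Predictability is about 66–72% with one fully informed enroller, about 53–60% with two or three assistants who do not share assignments, and 50% with none informed, all for assumed block sizes of 2 to 10. The bias is unknown because steering is unknown; 0.10 SD with 6.6% error, and 0.20 SD with 11%, are illustrations for one fully informed enroller. This is a cheap improvement to the design, not evidence that allocation was subverted.

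**What to change.** For any patient still to be randomised, replace the on-site envelopes in 3.6.1 with release of the arm by REDCap. The Applied Health Research Centre should hold the list, and the arm should be shown only after consent, confirmed eligibility and the week-0 surveys are saved for that study ID. Delete the claim that undisclosed block sizes ensure concealment.

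Random permuted blocks may be kept. Central release then prevents envelope handling and early opening, but it does not remove guessing from past assignments, and 3.6.1 should state that residual risk. An unrestricted sequence would remove it, at an expected efficiency loss of about 1.4% and about a 4% chance of a split of 26/44 or worse among 70. That is a trade-off for the sponsor, not a requirement.

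The cost is a short amendment and some REDCap set-up by the group already building the database. The benefit depends on timing: 3.5.7 gives January to December 2018 for recruitment, and this version is dated April 2019, so few or no patients may remain. Testing afterwards whether week-0 RPQ tracks the tally-predicted arm is a weak substitute. About 0.59 × 70 ≈ 41 enrolments would have an uneven tally, roughly 20 per predicted arm, which gives only about 35% power even for a 0.50 SD contrast. A null result would not be reassuring.
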